3. BACKGROUND

Deprescribing (i.e., discontinuing medication) is an important part of palliative care to prevent polypharmacy, which is associated with increased risk of adverse drug events, drug-drug and drug-disease interactions, reduced functional capacity, multiple geriatric syndromes, medication nonadherence, and higher healthcare costs. One of the most widely used cardiovascular drug classes in cancer patients in a palliative setting are antithrombotics, including anticoagulant and anti-platelet agents. Antithrombotic drugs, e.g., (DOACs), low-molecular-weight heparins (LMWH), vitamin-K antagonists (VKA) and so-called antiplatelet agents (such as acetyl salicylic acid and P2Y12 inhibitors), are indicated in patients with prosthetic heart valves, in those with venous thromboembolism (VTE), for stroke prevention in atrial fibrillation as well as in patients with established atherosclerotic cardiovascular disease (such as myocardial infarction, stroke, or peripheral artery disease). Most patients have been receiving these drugs chronically before their cancer was diagnosed, whilst others are being prescribed them in order to treat or prevent cancer-associated thrombosis. Obviously, decisions on deprescribing antithrombotics heavily depend on the indication of the antithrombotic drug in addition to patient and healthcare professional preferences and experience, and on the estimated life expectancy of the patient.

Understanding current patterns of management of antithrombotic therapy (ATT) as well as the rationale and preferences behind these patterns is crucial for improving clinical practice. Since deprescribing patterns and rationale may largely differ across countries, relevant data at a large scale is needed to fully understand and appreciate the relevant decision processes.

The insights gained in this study are a first step towards the development of a clinical decision tool supporting decisions on ATT in cancer patients.

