15.4 Survey: Questions on actual case decisions

In the following (multiple choice) questions, you will be asked to describe one to three actual cases of patients with active cancer, who were considered to receive end-of-life care, in which you considered deprescription of antithrombotic medication.

1. Please select the age category of the patient (*< 40 years; 40-75 years; 75 years or older*)
2. Please indicate the type of antithrombotic medication involved (*DOAC; VKA; LMWH (therapeutic); antiplatelet agent*)
3. Please select the indication of the antithrombotic medication (*atrial fibrillation; treatment of acute VTE-event, prevention of (recurrent) VTE; mechanical heart valves; other indication (free text)*)
4. Please indicate the patient's performance status (*ECOG-PS grade 0-2, ECOG-PS ≥ 3*)
5. Please indicate the estimated prognosis of the patient at the time of consideration (*< 6 months; < 3 months; < 2 weeks*)
6. Please specify the setting of the patient at the time of consideration (*at home without palliative care; at home with palliative care; at rehabilitation facility; at nursing facility; at hospice facility; in 'acute care' setting; other (free text)*).
7. Please select one or more of the attributes that played a role in your consideration of deprescribing the antithrombotic medication; multiple answers are possible (*type of antithrombotic medication; indication of the antithrombotic medication; bleeding risk; thrombotic risk; sex; age; patient's performance status; patient's preference; other (free text)*).
8. Did you decide to deprescribe the antithrombotic treatment? (*yes; no*)

9. If no:

Which of the following attributes made you decide not to deprescribe the antithrombotic drugs? Multiple choices are possible.

Experience with deprescribing: not enough; enough

Symptom burden: high

Burden of medication (administration): low

Thrombotic risk: high

Bleeding risk: low

Antithrombotic medication indication: atrial fibrillation; acute VTE-event, prevention of (recurrent) VTE; mechanical heart valves; other indication (free text)

Sex: male; female, other (selection to be made)

Age: (< 40 years; 40-64 years; 65-74 years; 75 years or older)

Patient's performance status: ECOG-PS 0-2

Patient's prognosis: < 2 weeks; < 3 months; < 6 months (selection to be made)

Patient's preference: continue antithrombotic treatment

Other (free text)

10. If yes:

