Which of the following attributes made you decide to deprescribe the antithrombotic drugs?

Multiple choices are possible.

Experience with deprescribing: enough

Symptom burden: low

Burden of medication (administration): high

Thrombotic risk: low

Bleeding risk: high

Antithrombotic medication indication: atrial fibrillation; acute VTE-event, prevention of (recurrent) VTE; mechanical heart valves; other indication (free text)

Sex: male; female, other (selection to be made)

Age: (< 40 years; 40-64 years; 65-74 years; 75 years or older)

Patient's performance status: ECOG-PS grade ≥ 3

Patient's prognosis: < 2 weeks; < 3 months; < 6 months (selection to be made)

Patient's preference: stop antithrombotic treatment

Other (free text)

Tumour-specific

11. Please select the type of cancer (*breast; lung; upper gastro-intestinal (GI); lower GI; endocrine; genito-urinary tract; brain; haematological; skin (excluding squamous/basal cell carcinoma); combination (select more than one); other (free text)*)
12. Please select the stage of cancer (*localized; regional; distant metastasis; not applicable*)
13. Please select the cancer treatment at the time of consideration/decision – multiple options possible (*none; surgery (in the previous 3 months); radiation therapy (in the previous month); chemotherapy (in the previous month); immunotherapy (in the previous month)*)
14. Please select the line of cancer treatment (*first-line, second-line, third-line, fourth-line, not applicable*)

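### The case-form drug list has no 'other' and no stated multi-select, and one yes/no cannot show a partial stop in patients on more than one antithrombotic

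*Combined protocol and SAP*

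**What the plan says.** Section 15.4 collects one to three real cases per professional. A case qualifies if the patient had active cancer, was considered to be in end-of-life care, and was one "in which you considered deprescription of antithrombotic medication". Neither the number of antithrombotic drugs nor the dose level is restricted.

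Question 2 reads "Please indicate the type of antithrombotic medication involved" and gives the options "DOAC; VKA; LMWH (therapeutic); antiplatelet agent". Nothing else is offered. Other items in the section are more open: question 7 states that "multiple answers are possible", question 13 that "multiple options possible", and questions 9, 10 and 11 also allow more than one answer. Questions 3, 6, 7, 9, 10 and 11 have a free-text 'other'.

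Question 8 asks "Did you decide to deprescribe the antithrombotic treatment", answered yes or no. Questions 9 and 10 then ask for the reasons for not stopping or for stopping. No item asks which drug was stopped.

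On scope, the Background (section 3) introduces the drug classes as examples. It says that some patients have taken them for years, "whilst others are being prescribed them in order to treat or prevent cancer-associated thrombosis". Question 3 includes prevention of VTE among the indications, with the word for recurrence in brackets.

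**The concern.** The first objective (section 4) is to describe how antithrombotic therapy is used at the end of life. Section 10 names the type of therapy among the case data, and the stop decision is the outcome of each case. Both variables depend on questions 2 and 8.

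A case that does not fit question 2 can go three ways: the respondent picks the nearest class, leaves the item blank, or does not enter the patient. The first puts a wrong value in the data and the second loses it. The third undermines the consecutive sampling that sections 8 and 10 ask for.

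For a patient on two drugs of whom one was stopped, both yes and no are defensible answers to question 8. The patient data are anonymised and the analysis in section 13 is descriptive, so the plan has no step that would recover or correct this later.

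**Working it through.** **The planned number of cases.** From section 8: 8 countries × 100 professionals = 800, and 800 × 3 cases = 2400. The plan's own maximum is reproduced. With one case per professional the figure is 800.

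**Who is affected, read from the form.**

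| Patient | Question 2 | Question 8 |
|---|---|---|
| One listed drug | Recorded correctly | Clear: the drug in question 2 was stopped or not |
| One drug outside the list | No correct answer available | Clear, but attached to a wrong or missing drug type |
| Two drugs of different classes, only one answer allowed | One drug lost | A partial stop may be coded yes or no |
| Two drugs of different classes, several answers allowed | Both recorded | A partial stop may be coded yes or no |
| Two antiplatelet agents | One tick at most under either format | A partial stop may be coded yes or no |

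The Background names two kinds of antiplatelet agent, so the last row is possible within the plan's own terms. The missing 'other' and the unrecorded partial stop remain whichever format the electronic form uses.

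**Number of cases.** The documents give no share, so this is an assumed range of 2% to 20%:

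- of 800: 0.02 × 800 = 16 to 0.20 × 800 = 160
- of 2400: 0.02 × 2400 = 48 to 0.20 × 2400 = 480

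**What this could do to a drug-specific stop rate.** Every input here is assumed. Question 2 is single choice, 30% of single-drug cases are antiplatelet, and half of the combination cases are filed there. The true yes rate is 40% for a single antiplatelet and 60% to 70% for combinations. With N cases and combination share s:

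shift = m / (n + m) × (combination rate − 40%), where n = 0.3 × N × (1 − s) and m = 0.5 × N × s.

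For N = 2400 and s = 10%, n = 648 and m = 120, so m / (n + m) = 120 / 768 = 0.156. The shift is 0.156 × 20 = 3.1 points to 0.156 × 30 = 4.7 points. The same formula gives 1.6 to 2.4 points at s = 5% and 5.9 to 8.8 points at s = 20%.

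The 95% half-width, 1.96 × √(p(1 − p) / (n + m)), is about 3.5 points for N = 2400 and about 6 points for N = 800. It treats cases as independent, although up to three come from one professional. On these inputs the shift can pass the sampling error from a combination share of about 10% at 2400 cases, and of about 20% at 800 cases.

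**The case against.** Five points can be made for the plan.

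- **Most cases may be fine.** A reader might infer that question 8 never shows which drug was stopped. That is not so: for a patient on one listed drug, questions 2 and 8 together identify it.
- **Question 2 may mean the drug under consideration.** The section is about cases where stopping was considered, and question 2 asks for the medication involved. On that reading the recorded class is right and question 8 refers to that drug. The reading is natural, but the form does not state it, and the other drug is still lost. It means that forced misclassification cannot be asserted as a general result.
- **The answer format is not settled.** Section 15.4 describes its questions as multiple choice, and the electronic form is not shown. The contrast with items that announce several answers suggests single choice but does not prove it.
- **Therapeutic LMWH may be a deliberate limit.** The same label appears in sections 15.2.1 and 15.3. A reader might infer from the Background and question 3 that preventive-dose LMWH is in scope and is being misrecorded. The Background is not an eligibility rule, however, and preventing VTE is also compatible with the listed anticoagulants. What stands is an unclear scope.
- **No size is documented, and no comparison of drug classes is named.** Both are true. Section 13 promises descriptive results by predefined subgroups and does not mention drug class. The documents also name no agent outside the four classes; the possibility follows from the Background's list being open-ended.

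These points narrow the concern. They do not supply a place to record an unlisted agent or a partial stop.

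**Conclusion.** The concern holds in a limited form. An unlisted agent cannot be recorded correctly, co-medication may be lost, and a partial stop cannot be distinguished from a full stop or no stop. Patients on a single listed drug are unaffected.

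The size is unknown. The ranges above show what assumed shares would imply and are not estimates. The shift in the antiplatelet stop rate needs the further assumptions of single choice and of combinations being filed half under antiplatelet.

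The documents do not support saying that a given number of cases will carry a wrong drug class, or that patients on preventive-dose LMWH are in scope and misrecorded. This is an inexpensive improvement to the form and does not undermine the study.

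**What to change.** Before the form opens:

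1. State in question 2 that all antithrombotic drugs at the time of consideration may be ticked, and add 'other (free text)'. Tell respondents to use that field for a second agent of the same class.
2. When more than one drug is ticked, add one item after question 8 asking which were stopped, with 'none' as an option. Show it whichever way question 8 is answered.
3. Reconcile the therapeutic LMWH option with the references to prevention in question 3 and the Background. Either add a recording option for non-therapeutic LMWH, or state in the case instructions that such use is out of scope. Which of the two applies is for the sponsor to decide.

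The cost is one further item for patients on combined therapy, in up to three cases per respondent, and free text to code. The planned numbers do not change. The reasons in questions 9 and 10 would still be recorded per case and not per drug; splitting them would lengthen the form considerably more.

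If the survey has already been run, the report should say how question 2 was set up, give the number of blank answers, and state that partial stops could not be identified.

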stage, time point in the course of the disease when the conversation about discontinuation of ATT took place, type and indication of ATT) will be collected via multiple-choice questions.

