11. REGULATORY AND LEGAL REQUIREMENTS

As confirmed by the responsible ethics committee, due to the non-interventional nature of this study and since no personal data of patients will be recorded or processed, professional advice and/or submission of this protocol to the ethics committee before commencement of the survey is not required.

Data privacy of participating healthcare professionals will be taken into account in accordance with the European General Data Protection Regulation (GDPR). With the exception of the e-mail addresses of survey participants for the purpose of forwarding the survey link and information on survey launch and completion, no personal data will be stored or processed. As detailed in the information for prospective participants, participants implicitly consent to the use of their e-mail addresses for said purposes by pre-registering.

Data on patients will be sufficiently coarsened such that no identification will be possible. As an additional security measure, this part of the survey will be exported and analyzed separately from the other two sections (s. section 9 above).

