15.2 Survey: General questions

1. When do you consider a patient in end-of-life care? If the life expectancy is:
A. < 1 year B. < 6 months C. < 3 months D. < 2 weeks
2. When a patient is considered to be in end-of-life care, I **XXX** prescribe antithrombotic medication upon the diagnosis of a thrombotic complication.
A. never B. sometimes C. often D. always
3. Have you ever deprescribed (i.e., terminated) antithrombotic medication in end-of-life care of cancer patients?
A. no B yes

In case of no, the participant will not be redirected to certain questions.

4. When a patient is considered to be in end-of-life care, I **XXX** deprescribe antithrombotic medication.
A. never B. sometimes C. often D. always
5. Give an estimate of the frequency per year that you consider deprescribing antithrombotic medication in patients, considered to be in end-of-life care:
XXX /year
6. Give an estimate of the frequency per year that you actually deprescribed antithrombotic medication in patients considered to be in end-of-life care:

XXX /year

7. Do you discuss deprescription of antithrombotic medication in patients at the end of life with colleagues?
A. never B. sometimes C. frequently D. always
8. Please indicate what factors determine whether you prescribe antithrombotic medication in patients considered to be in end-of-life care.
9. Please indicate what factors determine whether you deprescribe antithrombotic medication in patients considered to be in end-of-life care.

15.2.1 Examples of factors relevant to questions 8 and 9

1. Antithrombotic medication:
 - DOAC or VKA
 - LMWH (therapeutic)
 - Antiplatelet agent
2. Indication for antithrombotic medication:
 - Atrial fibrillation
 - Treatment of acute VTE event or prevention of (recurrent) VTE
 - Mechanical heart valves
 - Other indication
3. Bleeding risk:
 - Low
 - High
4. Thrombotic risk:
 - Low
 - High
5. Sex:
 - Female
 - Male
 - Other
6. Age:
 - < 40 years
 - 40-75 years
 - > 75 years
7. Patient's performance status:
 - Eastern Clinical Oncology Group performance status (ECOG-PS) grade 0-2
[Oken MM et al. Am J Clin Oncol. 1982]
 - ECOG-PS grade ≥ 3
8. Patient prognosis:
 - < 6 months
 - < 3 months
 - < 2 weeks

9. Patient preference:

- Stop antithrombotic treatment
- Continue antithrombotic treatment

10. Other

Free text

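### As printed, the case-level indication item most naturally combines treatment of acute VTE with prevention of (recurrent) VTE, and no other case item recovers the distinction

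*Combined protocol and SAP*

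**What the plan says.** Section 15.4 asks each participant to describe one to three real cases. Question 3 records the indication: "atrial fibrillation; treatment of acute VTE-event, prevention of (recurrent) VTE; mechanical heart valves; other indication (free text". Questions 9 and 10, which ask for the reasons for continuing or stopping, carry a near-identical line: "Antithrombotic medication indication: atrial fibrillation; acute VTE-event, prevention of (recurrent) VTE; mechanical heart valves; other indication (free text". In 15.2.1, the list of factors for general questions 8 and 9, the category is one bullet: "Treatment of acute VTE event or prevention of (recurrent) VTE".

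Section 3 states that "decisions on deprescribing antithrombotics heavily depend on the indication of the antithrombotic drug". It also describes patients who were on these drugs before their cancer, "whilst others are being prescribed them in order to treat or prevent cancer-associated thrombosis".

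The patient data listed in section 10 end with "time point in the course of the disease when the conversation about discontinuation of ATT took place, type and indication of ATT". The drug item, question 2 of 15.4, offers "DOAC; VKA; LMWH (therapeutic); antiplatelet agent". Section 13 plans a descriptive main analysis by predefined subgroup with 95% confidence intervals.

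**The concern.** The VTE answer can hold up to three situations: treatment of a recent clot, prevention of recurrence after an earlier one, and (because 'recurrent' is in brackets) prevention in a patient who never had a clot. The protocol treats indication as a main driver of the decision to stop. If clinicians stop at different rates in these situations, the VTE stop share is an average whose weights nobody recorded. Two countries, specialties or drug classes with the same practice could then show different VTE figures, and real differences in practice could be hidden. No analysis can repair this afterwards, because the separating variable would not be in the data.

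The example choice scenarios in 15.3 vary performance status, thrombotic risk, bleeding risk and drug class, but not indication. On those examples, the real cases are the main place where a stop decision can be related to its indication.

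**Working it through.** The plan gives no figure on this point, so there is none to reproduce. The check has three parts.

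**1. One option or two?**

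- Within question 3, semicolons separate the entries, and the acute-treatment and prevention wording sits between two of them, joined by a comma. That gives four options, of which VTE is one.
- Section 15.2.1 prints the same content as one bullet joined by 'or'.
- Against this, 15.4 uses commas between distinct answers elsewhere: question 4 (the two ECOG groups), question 14 (lines of treatment) and the sex line in questions 9 and 10. Section 15.2.1 also joins DOAC and VKA in one bullet, while question 2 of 15.4 lists them separately.

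One option is the natural reading, but not a certain one. If two were intended, acute treatment stands alone, but prevention with and without a previous VTE still share an answer.

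**2. Does another case item recover the split?**

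| Items in 15.4 | What they record | Separates the VTE situations? |
|---|---|---|
| 1, 4, 5, 6 | Age, performance status, prognosis, setting | No |
| 2 | Drug class | No: the listed anticoagulants are not tied to treatment or prevention |
| 7 | Factors considered | No: thrombotic risk is only a factor to tick |
| 8 | Stopped or not | No |
| 9, 10 | Reasons | No: same grouping; thrombotic risk appears as a reason, not as a recorded characteristic |
| 11–14 | Tumour type, stage, treatment, line | No |

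The only time point named in section 10 is that of the conversation about stopping, not of the VTE. The free text in question 3 belongs to 'other indication', which a VTE case would not need.

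**3. What pooling can do (illustration, all rates and mixes assumed)**

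Let w be the proportion of VTE cases that are acute treatment, and let p_a and p_p be the stop shares for acute treatment and prevention. The pooled share is P = w × p_a + (1 − w) × p_p.

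Assume p_a = 20% and p_p = 60%:

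- 70:30 mix: 0.7 × 20% + 0.3 × 60% = 14% + 18% = 32%.
- 30:70 mix: 0.3 × 20% + 0.7 × 60% = 6% + 42% = 48%.
- Difference under identical practice: 48% − 32% = 16 points.
- Range: P falls from 56% at w = 0.1 to 24% at w = 0.9.

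In general, the gap between two groups with the same practice is (w₁ − w₂) × (p_a − p_p). With the same two mixes but assumed stop shares of 35% and 45%, its size is 0.4 × 10 = 4 points. It is zero if the stop shares are equal or the mixes are equal.

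Nor does a pooled share identify its components. A pooled 50% arises from 50% and 50% at any mix, or from 10% and 90% at w = 0.5 (0.5 × 10% + 0.5 × 90% = 50%).

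**Precision after splitting acute treatment from all prevention.** Assume that 20–40% of cases are VTE and 20–50% of those are acute. Take a stop share of 50% and ignore clustering within professional. The 95% half-width is 1.96 × √(0.25/n). The planned numbers give 800 × 1 = 800 to 800 × 3 = 2400 cases. The smallest cells in that range are:

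| Cases | Smallest acute cell | Half-width | Smallest prevention cell | Half-width |
|---|---|---|---|---|
| 800 | 800 × 0.2 × 0.2 = 32 | 17.3 points | 800 × 0.2 × 0.5 = 80 | 11.0 points |
| 2400 | 2400 × 0.2 × 0.2 = 96 | 10.0 points | 2400 × 0.2 × 0.5 = 240 | 6.3 points |

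A separate cell for prevention without a previous VTE would be smaller still.

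**The case against.** The strongest reply is that the wording may be no more than loose punctuation in an appendix, and that how finely to divide an indication is a design preference. The part about punctuation stands: the one-option reading is not proven. It does not remove the point, because a two-option reading still merges the two kinds of prevention, and ambiguous options need clarifying in any case.

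Three stronger readings are tempting and should be resisted.

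- *That section 3 itself separates treating from preventing.* It does not. It names the two together, as reasons for prescribing in cancer, and contrasts both with drugs taken before the cancer. Its list of indications gives VTE once.
- *That the planned decision tool could not use the result.* Section 3 calls the study a first step towards a tool. A pooled VTE share is coarser, not unusable; it cannot tell treatment from prevention.
- *That a 16-point bias has been shown.* The figure rests wholly on assumed rates and mixes. Section 13 names no comparison of countries, professions or drug classes within VTE, although section 3 expects practice to differ between countries.

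It is also fair to say that the documents do not show how common prevention without a previous VTE is among these cases. The drug item lists LMWH only as therapeutic, so some such cases may have no matching drug answer.

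Privacy could be offered as the reason for broad categories: "Data on patients will be sufficiently coarsened such that no identification will be possible". That statement is general and not tied to this item. The survey already asks for tumour type, stage, recent treatment and treatment line, so two more indication categories add little detail by comparison.

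Small cells are a real cost, but a reversible one. Separate answers can be pooled later; a combined answer cannot be split.

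**Conclusion.** The point holds in a limited form. As printed, the indication item most naturally merges acute VTE treatment with VTE prevention; on either reading it merges prevention with and without a previous VTE. No other case item restores the distinction.

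The consequence is conditional. If stop shares differ between these situations, the pooled VTE share reflects an unrecorded mix. That they differ is a reasonable judgement, supported only indirectly by the protocol's statement about indication. On the assumed 20% and 60%, mixes of 70:30 and 30:70 give 32% and 48%; equal stop shares or equal mixes give no distortion between groups. The loss concerns the descriptive analysis of real cases and the reasons given in questions 9 and 10. It does not invalidate the study, but it is avoidable and worth correcting before launch.

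**What to change.** Before launch, replace the VTE entry in question 3, in the indication lines of questions 9 and 10, and in 15.2.1 with three separate options: treatment of acute VTE; prevention of recurrent VTE (previous VTE); prevention of VTE (no previous VTE). Use one separator throughout each list so that the number of options is not in doubt. In section 13, state that the stop share will be reported for each with its 95% confidence interval, and that categories will be pooled where numbers are small.

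The cost is two extra answer options in existing multiple-choice items, and smaller cells. With the assumptions above, the acute and all-prevention cells mostly remain usable for overall description; breakdowns by country would often need pooling.

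### The indication lists have no named option for atherosclerotic cardiovascular disease, so those cases fall into a mixed 'other' category (minor; a free improvement before launch)

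*Combined protocol and SAP*

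**What the plan says.** Section 3 sets the scope as "antithrombotics, including anticoagulant and anti-platelet agents". It names four groups of indications: prosthetic heart valves, VTE, stroke prevention in atrial fibrillation, and a fourth group introduced as "as well as in patients with established atherosclerotic cardiovascular disease (such as myocardial infarction, stroke, or peripheral artery disease". It then says that the choice to stop these drugs depends strongly on why they were prescribed.

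Section 10, part c, says that type and indication of therapy in the actual cases are obtained through multiple-choice items. The lists themselves are in the appendices:

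- **15.2.1, item 2**, headed "Indication for antithrombotic medication": atrial fibrillation; "Treatment of acute VTE event or prevention of (recurrent) VTE"; mechanical valves; a residual option without a text field.
- **15.4, question 2** (drug type): DOAC, VKA, therapeutic LMWH, antiplatelet agent.
- **15.4, question 3** (indication): atrial fibrillation, then "treatment of acute VTE-event, prevention of (recurrent) VTE; mechanical heart valves; other indication (free text".
- **15.4, questions 9 and 10** (reasons for not stopping and for stopping): "Antithrombotic medication indication: atrial fibrillation; acute VTE-event, prevention of (recurrent) VTE; mechanical heart valves; other indication (free text".

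All three indication lists in 15.4 thus close in the same way: "mechanical heart valves; other indication (free text".

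Section 13 describes the main flash mob analysis as descriptive. It does not say how free-text answers will be coded.

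**The concern.** The case form lets a respondent record an antiplatelet agent as the drug. It offers no named answer for the one Background indication group that is missing from every list. The plan itself treats indication as a leading explanatory factor, and it intends to collect it as a structured answer. For one of its four groups the structured answer does not exist.

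What is at stake is how clearly the descriptive results can be read. A stopping rate reported for 'other' would mix atherosclerotic disease with everything else that lacks a name. The same holds for the stated reasons in questions 9 and 10. Separating the atherosclerotic cases would take manual coding under a rule not yet written, and would depend on what respondents chose to type during a seven-day collection window.

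**Working it through.** The plan states no figure on this point, so the main check is a comparison of lists. An illustration of size follows.

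**Step 1. Background groups against answer options**

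| Indication group in Section 3 | 15.2.1 item 2 | 15.4 Q3 | 15.4 Q9 | 15.4 Q10 |
|---|---|---|---|---|
| Atrial fibrillation | named | named | named | named |
| VTE | named | named | named | named |
| Prosthetic valves | mechanical only | mechanical only | mechanical only | mechanical only |
| Atherosclerotic cardiovascular disease | none | none | none | none |
| Residual option | yes, no text field | yes, free text | yes, free text | yes, free text |

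Atherosclerotic disease is the only group without a named option, and it is absent from all four lists. The residual is mixed: the Background speaks of prosthetic valves and the lists of mechanical ones, so a non-mechanical prosthesis would also be entered there.

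**Step 2. One VTE option or two**

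Item 2 of 15.2.1 joins acute treatment and prevention with 'or', which makes one option. In 15.4 question 3 a comma stands between them, while semicolons separate the other answers; that suggests one option. But the same questionnaire separates distinct answers by commas in question 4 (the two performance-status grades) and question 14 (lines of treatment); that suggests two. The text does not settle it.

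**Step 3. Possible size**

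Inputs from Section 8:

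- At least 800 professionals, from 8 countries × 100 = 800.
- One to three cases each, so 800 × 1 = 800 cases, up to 800 × 3 = 2400. The upper figure agrees with the plan's 2400.

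Inputs not in the documents, taken as assumptions:

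- Share of cases that involve an antiplatelet agent: 10% to 40%.
- Share of those with an atherosclerotic indication: 50% to 90%.

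Formula: affected cases = number of cases × antiplatelet share × atherosclerotic share.

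| | Share of all cases | Of 800 | Of 2400 |
|---|---|---|---|
| Low end | 0.10 × 0.50 = 5% | 40 | 120 |
| High end | 0.40 × 0.90 = 36% | 288 | 864 |

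The width of this range reflects the absence of any frequency in the documents. The gap in the lists does not depend on it.

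**The case against.** The strongest reply is that the information is captured. Questions 3, 9 and 10 of 15.4 all allow free text with the residual option, and question 2 records the drug type separately. A cross-table of antiplatelet agent by 'other' would isolate most of the candidate cases before any text is read. The flash mob analysis is descriptive, Section 13 specifies no analysis by indication, and neither objective in Section 4 fails because of this list. The list in 15.2.1 is headed as examples, and its item 10 does offer free text.

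Most of this stands, and it is why the point is minor. Three things remain. The cross-table gives candidates, not the indication itself, and misses an atherosclerotic case recorded under another drug type. Free text helps only as far as respondents write something usable, and no coding rule is planned. The general text field at item 10 of 15.2.1 does not prompt someone who has ticked the residual under item 2 to say what it was.

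A reader might infer more than the documents support:

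- **That every antiplatelet case ends up in 'other'.** Section 3 assigns no indication to a drug class and gives no frequencies, so an estimate needs a second assumption about the atherosclerotic share.
- **That the discrete choice experiment is damaged.** The example scenarios in 15.3 vary performance status, thrombotic risk, bleeding risk and drug type. Indication is not an attribute there, so this gap leaves them untouched.
- **That the gap undermines the assurance of anonymity in Section 11.** Free text already appears in several other questions of 15.4 and would remain after the fix.
- **That VTE treatment and prevention are merged throughout.** This is clear only in 15.2.1.

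**Conclusion.** The point holds as a minor weakness of the instrument. One of the plan's four indication groups has no named answer in any of the four lists, although antiplatelet agents are a study drug class and the plan gives indication great weight. The consequence is classification into a mixed residual: recoverable by hand-coding in 15.4, and possibly not specified at all under item 2 of 15.2.1.

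Under the two assumed shares, 10-40% antiplatelet use and 50-90% of that atherosclerotic, 5-36% of cases are affected: 40-288 if 800 cases are returned, 120-864 if 2400 are. These counts illustrate a range and do not forecast a number. The documents do not support saying that the data are lost or that results by indication would be impossible.

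**What to change.** Before the survey opens:

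1. Add established atherosclerotic cardiovascular disease as a named option in 15.2.1 item 2 and in 15.4 questions 3, 9 and 10.
2. Use one identical indication list in all four places.
3. State whether acute VTE treatment and VTE prevention are one option or two, and punctuate the lists to match.
4. Add a sentence to Section 13 on how the remaining free-text indications will be coded.

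The cost is one or two extra answer options and a sentence of text. Sample size, survey length and the choice scenarios stay essentially as they are, and less recoding is needed afterwards. If the survey has already run, the structured answer can no longer be obtained. In that case, write the coding rule for 'other' before looking at stopping rates by indication, and report the recoded atherosclerotic group separately from the rest of 'other'.
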